7.4 Efficacy Assessments

Study evaluations will take place in accordance with the flow charts in Section 5. Baseline disease assessments should be performed within 28 days prior to the first dose utilizing CT or MRI. In addition to neck, chest, abdomen, pelvis, and brain, all known sites of disease should be assessed at baseline. Subjects will be evaluated for progression of target lesions or for development of new metastases beginning 12 weeks (+/- 7 days) relative to the first dose of study treatment, and will continue to have surveillance assessment every 12 weeks (+/- 7 days) for the first 12 months. From > 12 months to 24 months after randomization, efficacy assessments should be every 12

weeks (+/- 14 days). From > 24 months until Year 5 after first dose of study treatment, efficacy assessments should be performed every 6 months (+/- 4 weeks).

7.4.1 Definitions

Progression is defined as progressive tumor lesions per immune-related RECIST (irRECIST) definition, or appearance of one or more new Merkel cell carcinoma lesions, which can be local or distant in location from the irradiated lesions.

Local Control of Irradiated Lesion:

Progression of the irradiated tumor lesion is associated with aggressive tumor biologic features and resistance to radiation therapy.

Measurable Disease per irRECIST:

Measurable lesions must be accurately measured in at least one dimension (longest diameter in the plane of the measurement to be recorded) with a minimum size of:

- 10 mm by CT/MRI scan - (CT/MRI scan slice thickness no greater than 5 mm)
- 10 mm caliper measurement by clinical examination (lesions which cannot be accurately measured with calipers should be recorded as non-measurable)
- 20 mm by chest x-ray.

Malignant lymph nodes: to be considered pathologically enlarged and measurable per RECIST 1.1, a lymph node must be ≥ 15 mm in short axis when assessed by CT scan (CT scan slice thickness recommended to be no greater than 5 mm).

If the measurable disease is restricted to a solitary lesion (visceral or nodal), its neoplastic nature must be confirmed either by cytology/histology or by lesion progression certified on the next CT/MRI examination.

Nonmeasurable Disease per irRECIST:

Nonmeasurable lesions include all other lesions, including small lesions (longest diameter < 10 mm or pathological lymph nodes with ≥ 10 and < 15 mm short axis), as well as truly nonmeasurable lesions. Lesions considered truly nonmeasurable include: leptomeningeal disease, ascites, pleural or pericardial effusions, inflammatory breast disease, lymphangitic involvement of skin or lung, abdominal masses/abdominal organomegaly identified by physical exam that is not measurable by reproducible imaging techniques.

7.4.2 Methods of measurements

- CT and MRI are an essential part of the work-up to establish recurrence. Conventional CT with IV contrast and MRI gadolinium should be performed with contiguous cuts of 10 mm or less slice thickness. Spiral CT should be performed using a 3- or 5-mm contiguous reconstruction algorithm; this specification applies to the tumors of the chest, abdomen and pelvis while head & neck tumors and those of the extremities usually require specific protocols. In each institute the same technique for CT/MRI should be used to characterize each new lesion.
- PET alone will not be considered for the disease assessment. Complementary CT and/or MRI

or biopsy must be performed in such cases.

- Cytology and/or histology are mandatory to confirm progression in doubtful lesions, cutaneous, subcutaneous or lymph node lesions. Histological or cytological evidence of progression should be attempted in all cases except for brain metastases.
- Clinically detected new lesions:
 - Superficial cutaneous lesions: the neoplastic nature must be confirmed by cytology/histology.
 - Deep subcutaneous lesions and lymph node lesions should be documented by ultrasound and histological/cytological evidence should be attempted. In absence of pathology report, lesion will be documented with a CT scan/MRI.
- Tumor markers or auto-antibodies alone cannot be used to assess disease progression.

7.4.3 Date of Progression

The first date when progression was observed is taken into account regardless the method of assessment. Therefore progression will be declared for any lesion when:

- Only imaging was performed and disease progression confirmed
- Only pathology was done and a new malignancy confirmed (in solitary or in doubtful lesions, cutaneous, subcutaneous or lymph node lesions)
- Both pathology and imaging were done and progression/malignancy confirmed. In this case, whatever examination come first its date is considered the date of relapse.

Note: for documentation, the date of progression is the date that the pathology and/or imaging confirms progression--not the date that the information was communicated to the subject.

7.5 Biobanking for Exploratory Correlative Studies

A variety of factors that could potentially predict clinical response to nivolumab will be investigated in peripheral blood and in tumor specimens taken from all subjects prior to treatment and as outlined in Section 7. Data from these investigations will be evaluated for associations with RFS, OS and distant metastasis-free survival and/or safety (adverse event) data. In addition, analyses of markers between the two treatment arms will provide the necessary data to identify and validate biomarkers with predictive vs prognostic value. All samples collected may also be used for future exploratory analyses (unless restricted by local requirements) to assess biomarkers associated with MCC or immunotherapy treatment. Complete instructions on the collection, processing, handling and shipment of all samples described herein will be provided in a separate procedure manual.

Tumor tissue and blood samples are crucial for correlative science studies to determine mechanisms by which SBRT and immunotherapy impact the anti-tumoral immune responses. A planned sample collection and preparation is necessary in order for these patient tissues can preserve integrity for future correlative biomarker studies. The collected samples may be assessed for correlative research to dissect underlying mechanisms of immune activation or tolerance in MCC or to discover novel therapeutic targets to enhance anti-tumoral immune responses using a variety of methodologies inclusive of, but not limited to ex vivo culture, flow cytometry, IHC, qRT-PCR, genetic mutation detection and fluorescent in-situ hybridization (FISH). The collected tissue will be stored at the MCC Tissue Core with the exception of fresh tumor tissue that will be

utilized for Merkel cell line establishment, which will be sent to the PI's laboratory.

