1.3.2 Secondary Objectives

- To compare the progression free survival (PFS) of nivolumab and ipilimumab versus SBRT plus nivolumab and ipilimumab in subjects with metastatic Merkel cell carcinoma.
- To compare the overall survival (OS) of nivolumab and ipilimumab versus SBRT plus nivolumab and ipilimumab in subjects with metastatic Merkel cell carcinoma.
- To evaluate the local control of irradiated tumor provided by SBRT in combination with nivolumab and ipilimumab
- To assess the overall safety and tolerability of nivolumab and ipilimumab versus SBRT plus nivolumab and ipilimumab in subjects with metastatic Merkel cell carcinoma.
- To evaluate whether PD-L1 expression is a predictive biomarker for ORR;
- To evaluate the Health Related Quality of Life (HRQoL) as assessed by European Organisation for Research and Treatment of Cancer (EORTC) QLQ-C30.

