1.3.3 Exploratory Objectives

- To evaluate associations between Merkel polyomavirus expression status and clinical efficacy (ORR, PFS and overall survival (OS))
- To explore potential biomarkers associated with clinical efficacy (ORR, PFS, and OS) and/or incidence of adverse events by analyzing biomarker measures within the tumor microenvironment and periphery (eg, blood, serum, plasma and PBMCs) in comparison to clinical outcomes
- To assess changes in health status and work and activity impairment in treatment groups using the EuroQol EQ-5D and the Work Productivity and Activity Impairment questionnaire (WPAI:GH), respectively.

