3.1 Inclusion Criteria

1. Signed Written Informed Consent

- Subjects must have signed and dated an IRB/IEC approved written informed consent form in accordance with regulatory and institutional guidelines. This must be obtained before the performance of any protocol related procedures that are not part of normal subject care
- Subjects must be willing and able to comply with scheduled visits, treatment schedule, laboratory tests, tumor biopsies, and other requirements of the study.

2. Signed Written Informed Consent

- All subjects must be either recurrent, unresectable or Stage IV AJCC (7th edition) and have histologically confirmed Merkel cell carcinoma with confirmed pathology in order to be eligible. Please refer to Appendix 1 or description of AJCC 7th editions of TNM and staging.
- At least 18 years of age
- ECOG PS < 2
- Active disease measurable by CT, MRI, or clinical exam
- Prior chemotherapy or immunotherapy will be allowed if new or persistent measurable site(s) of disease are present.
- Prior radiation therapy will be allowed if there is active measurable disease burden.
- All subjects must have at least 2 distinct lesions as documented by a complete physical examination or imaging studies within 4 weeks prior to randomization. Imaging studies must include a CT scan of the involved disease sites and all known sites of resected disease and brain magnetic resonance (MRI) or CT (brain CT allowable if MRI is contraindicated or if there is no known history of resected brain lesions).
- Tumor tissue from the core biopsy or resected site of disease must be provided for biomarker analyses. Prior surgery that required general anesthesia must be completed at least 4 weeks before study drug administration. Surgery requiring local/epidural anesthesia must be completed at least 72 hours before study drug administration.
- All baseline laboratory requirements will be assessed and should be obtained within 14 days of randomization. Screening laboratory values must meet the following criteria.

- i) WBCs $\geq 2000/\mu\text{L}$
- ii) Neutrophils $\geq 1500/\mu\text{L}$
- iii) Platelets $\geq 100 \times 10^3/\mu\text{L}$
- iv) Hemoglobin $\geq 9.0 \text{ g/dL}$
- v) Creatinine Serum creatinine $\leq 1.5 \times$ upper limit of normal (ULN) or creatinine clearance $> 40 \text{ mL/minute}$ (using Cockcroft/Gault formula)
- vi) AST $\leq 3 \times$ ULN
- vii) ALT $\leq 3 \times$ ULN

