9.2.2 Secondary Endpoint(s)

The first secondary endpoint is PFS. PFS will be programmatically determined based on the disease progression date provided by the investigator and is defined as the time between the date of randomization and the date of first progression (local, regional or distant metastasis) or death (whatever the cause), whichever occurs first. (Note: a subject who dies without reported progression will be considered to have progressed on the date of death.) For subjects who remain alive and whose disease has not progressed, PFS will be censored on the date of last evaluable disease assessment.

The second secondary endpoint (OS) is defined as the time between the date of randomization and the date of death. For subjects without documentation of death, OS will be censored on the last

date the subject was known to be alive. OS will be followed continuously while subjects are on the study drug and every 3 months via in-person or phone contact after subjects discontinue the study drug.

To third secondary endpoint to compare the local control of irradiated tumor provided by SBRT in combination with nivolumab versus nivolumab and ipilimumab will be assessed by the local control rate of the irradiated lesion.

The fourth secondary endpoint (to assess the safety and tolerability of nivolumab, SBRT and ipilimumab) will be measured by the incidence of adverse events, serious adverse events, deaths, and laboratory abnormalities.

The fifth secondary endpoint (to evaluate PD-L1 expression as a predictive biomarker) will be measured by the endpoint RFS based on PD-L1 expression level.

The sixth secondary objective (to evaluate HRQoL) will be measured by mean changes from baseline in the EORTC-QLQ-C30 global health status/QoL composite scale and by mean changes from baseline in the remaining EORTC QLQ-C30 scales in all randomized subjects.

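### The PD-L1 secondary endpoint is set as RFS, which the protocol never defines and which does not match the ORR objective; Sections 9.3.2.2 and 7.5 each specify something different again.

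*Combined protocol and SAP*

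**What the plan says.** Four places in the combined protocol and SAP bear on PD-L1 and the other biomarkers.

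- **Section 1.3.2 (repeated in the synopsis)** gives the secondary objective: "To evaluate whether PD-L1 expression is a predictive biomarker for ORR".
- **Section 9.2.2** gives the fifth secondary endpoint, tied to that objective. It "will be measured by the endpoint RFS based on PD-L1 expression level".
- **Section 9.3.2.2** gives the PD-L1 methods: a Cox model with a PD-L1-by-arm interaction for the primary and secondary endpoints; ORR within PD-L1-positive and PD-L1-negative subgroups, with log-rank tests and hazard ratios; and Kaplan-Meier PFS. It labels these analyses descriptive and unadjusted for multiplicity. It does not mention RFS.
- **Section 7.5**, on exploratory correlative work, says: "Data from these investigations will be evaluated for associations with RFS, OS and distant metastasis-free survival", and also lists safety. The exploratory objective in Section 1.3.3 is "To explore potential biomarkers associated with clinical efficacy (ORR, PFS, and OS") and/or adverse events.

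On entry status, Section 3.1 requires "Active disease measurable by CT, MRI, or clinical exam" and adds "All subjects must have at least 2 distinct lesions as documented by a complete physical examination or imaging studies".

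**The concern.** An endpoint should measure what its objective asks. Here the objective is about response and the endpoint is a relapse-free time. Relapse-free survival needs a disease-free starting point, and no eligible subject has one. The methods section then handles response with tools for time-to-event data.

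Whoever programs the analysis would have to decide, possibly with data in hand, whether the PD-L1 result is an RFS, PFS or ORR result, and by which model. With few PD-L1-negative subjects, that choice could change what is reported for a listed secondary endpoint.

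**Working it through.** The plan gives no figure to reproduce on this point, so the check is mainly a comparison of passages.

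**Step 1. Objective against endpoint against method.**

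| Place | Outcome for PD-L1 | Method |
|---|---|---|
| 1.3.2 and synopsis | ORR | none given |
| 9.2.2 | RFS | none given |
| 9.3.2.2 | ORR, plus PFS | Cox interaction, log-rank and hazard ratios; Kaplan-Meier for PFS |

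No two rows agree. A log-rank test or hazard ratio needs a time to event; ORR is a yes/no outcome per subject.

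**Step 2. Is RFS defined?** Section 9.2.2 gives start, event and censoring for PFS and OS. The PFS event is "the date of first progression (local, regional or distant metastasis) or death (whatever the cause), whichever occurs first". RFS has no such definition and is missing from the abbreviation list in Section 12, which does contain PFS, OS, EFS and DMFS. The only other use of RFS is in Section 1.4.9, for a cited study of resected melanoma with no evidence of disease, where the term fits.

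**Step 3. Could RFS apply?** The entry criteria leave no subject disease-free at randomization, so the number with a valid RFS starting state is zero.

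**Step 4. Section 7.5 against Section 1.3.3.** Section 1.3.3 names ORR, PFS, OS and adverse events. Section 7.5 names RFS, OS, distant metastasis-free survival and safety. OS and safety agree. ORR and PFS are missing from Section 7.5, and two outcomes that no objective names stand in their place. A subject with distant metastases at entry is not at risk of a first one.

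**Step 5. How small are the PD-L1 cells?** This matters for the choice of replacement method. Assume both arms reach the full 24 subjects (Section 9.1.1), so N = 48, and that every sample is evaluable. Section 1.2.1, Table 1, gives PD-L1 positivity of 53.8% overall (49 of 91) and 75% in Stage IV.

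- At 53.8% positive: 48 × 0.462 = 22.2, about 22 PD-L1-negative subjects, or 11 per arm.
- At 75% positive: 48 × 0.25 = 12, or 6 per arm.

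If negative subjects respond at the design rates of 17% or 40% (an assumption):

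| Negatives per arm | Expected responders at 17% | Expected responders at 40% | Chance of no responder at 17% | Chance of no responder at 40% |
|---|---|---|---|---|
| 6 | 6 × 0.17 = 1.0 | 6 × 0.40 = 2.4 | 0.83^6 = 0.33 | 0.60^6 = 0.05 |
| 11 | 11 × 0.17 = 1.9 | 11 × 0.40 = 4.4 | 0.83^11 = 0.13 | 0.60^11 = 0.004 |

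An empty cell is therefore quite possible, and an ordinary logistic interaction model would then have no finite estimate.

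**The case against.** A reader might infer more than the documents support, in five ways.

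*That the PD-L1 and response question would go unanswered.* It would not. Section 9.3.2.2 already plans ORR by PD-L1 subgroup and a PD-L1-by-arm interaction. The objective is specified in conflicting ways, not left out.

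*That RFS makes the endpoint beyond repair.* The protocol uses relapse and recurrence loosely for progression; Section 7.4.3, for instance, speaks of the date of relapse when fixing the date of progression. RFS may simply be a stray label for PFS, which is fully defined. This is a fair reading, though an inference. It removes the problem of the starting state but not the mismatch, since PFS is not ORR either.

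*That distant metastasis-free survival is impossible for everyone.* Section 3.1 admits recurrent or unresectable disease as well as Stage IV, so the outcome could apply to a subject without distant metastasis at entry. The documents do not say how many such subjects to expect. As an outcome of this trial it appears only in the exploratory text of Section 7.5, not in the PD-L1 endpoint.

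*That every biomarker association in Section 7.5 is invalid.* OS and safety are listed there and are sound.

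*That the trial's main conclusion is at risk.* The PD-L1 analyses are labelled descriptive, and the two-stage and Bayesian selection rules do not use them.

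All five limits stand. None reconciles Section 9.2.2 with Section 1.3.2, and none makes log-rank tests or hazard ratios suitable for ORR.

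**Conclusion.** The point holds in bounded form. The fifth of six secondary endpoints names an undefined outcome that differs from its objective, and the methods section adds a third specification that treats a binary outcome as a time to event. Section 7.5 has a smaller, exploratory version of the fault: two of its named outcomes are out of line with Section 1.3.3.

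For RFS the conclusion rests on the entry criteria and the absence of any definition, and it holds for every subject. For distant metastasis-free survival it holds only for subjects with distant metastases at entry. The cell sizes assume full accrual, complete PD-L1 data and positivity between 53.8% and 75%; they bear on the choice of method, not on whether the passages conflict. This should be corrected before the PD-L1 analysis is run.

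**What to change.** Change four places together, so that no conflict remains.

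- **Section 9.2.2:** make ORR the PD-L1 endpoint, with PFS and OS as supportive.
- **Section 9.3.2.2:** for ORR, replace the Cox, log-rank and hazard-ratio methods with response rates and exact confidence intervals by PD-L1 subgroup and arm, and a PD-L1-by-arm interaction from an exact or penalised (for example Firth) logistic model. Keep Cox and Kaplan-Meier methods for PFS and OS, and keep the descriptive label.
- **Section 7.5:** replace RFS and distant metastasis-free survival with ORR and PFS; keep OS and safety.
- **ORR itself:** use one definition throughout. The synopsis counts confirmed complete and partial responses, while Section 9.2.1 also adds stable disease. Until this is settled, ORR as the PD-L1 endpoint would still be ambiguous.

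The cost is wording. Baseline tumor tissue, response, progression and survival are already collected under Sections 3.1 and 7.1.

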- To assess the overall safety and tolerability of nivolumab and ipilimumab versus SBRT plus nivolumab and ipilimumab in subjects with metastatic Merkel cell carcinoma.
- To evaluate whether PD-L1 expression is a predictive biomarker for ORR.
- To evaluate the Health Related Quality of Life (HRQoL) as assessed by European Organisation for Research and Treatment of Cancer (EORTC) QLQ-C30.

Exploratory: See [Section 1.3.3](#) of the protocol.

Study Design:

This is a Phase 2, randomized, multi-institutional study of nivolumab and ipilimumab alone versus in combination with SBRT for subjects (≥ 18 years) with metastatic Merkel Cell Carcinoma. Approximately 50 subjects will be randomized 1:1 and stratified by prior immunotherapy exposure. Dose reductions will not be allowed.

Treatment Arms:

Randomized 1:1 [Arm A: Arm B]: Treatment until progression on either arm.

Arm A:

Nivolumab 240 mg IV over 30 min q2 weeks and Ipilimumab 1 mg/kg IV over 30 min q6 weeks until progression or unacceptable toxicity

Arm B:

Nivolumab 240 mg IV over 30 min q2 weeks and Ipilimumab 1 mg/kg IV over 30 min q6 weeks until progression or unacceptable toxicity

Radiation to be given at the start of week 2

- 8 Gy x3 doses in over ≤ 2 weeks

SBRT should begin the week following the first dose of nivolumab and ipilimumab. All sites other than skin should receive SBRT in consecutive days. Skin lesions can be treated every other day.

The number of lesions receiving SBRT will be at the treating physician's discretion based on anticipated toxicity. Larger or symptomatic lesions are of higher priority for SBRT. At least one target lesion will not receive SBRT, to evaluate ORR. The scatter radiation dose to this target lesion should be monitored if located less than 6cm from the irradiated lesions.

All subjects will be treated until progression of disease, unacceptable toxicity, or subject withdrawal of consent. Palliative radiation therapy will not be permitted while being treated under the protocol. The need for palliative radiation therapy will be considered progressive disease.

Study Population: Metastatic Merkel cell carcinoma subjects

Key Inclusion Criteria:

- At least 18 years of age
- ECOG PS < 2
- Active disease measurable by CT or MRI.
- Prior chemotherapy or immunotherapy will be allowed if new or persistent measurable site(s) of disease are present.
- Prior radiation therapy will be allowed if there is active measurable disease burden.

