1.4.4 Rationale for Two Experimental Arm Design

Merkel cell carcinoma is a rare malignancy with the incidence estimated to be approximately 0.3–0.6/100,000 in the US³¹. Merkel cell carcinoma is associated with a high rate of locoregional recurrence and the majority of patients die from distant metastasis. Survival rates at 5 years range from 23-80%.⁵⁻⁹ Despite the poor prognosis, the rarity of this cancer has limited conducting prospective,

randomized data guiding to guide treatment. Combined with aggressive behavior of this cancer refractory to most systemic agents, it has been a clinical challenge to define the standard of care in MCC. Most recently, a promising breakthrough for metastatic MCC came through PD1/PDL1 axis blockade^{36,37}. Despite excitement elicited by high response rate to PD1 blockade for metastatic MCC, further optimization to maximize the benefit of immunotherapy is of pivotal importance in this perhaps most aggressive and lethal skin cancer.

Therefore, we propose a randomized phase II trial in which both arms of the trial are experimental. By employing carefully designed two arm Simon's two stage design, we will compare both experimental arms with the historical control as well as each other. Preclinical and clinical evidence extrapolated from other solid malignancies including melanoma suggests improved therapeutic efficacy with acceptable additional toxicity in both proposed experimental arms. Such clinical trial design is not unprecedented. Indeed, even in NRG-HN002 trial, a randomized phase II trial for patients with p16 positive, non-smoking associated, locoregionally advanced oropharyngeal cancer (NCT02254278), a two arm experimental design has been used to expedite optimization of clinical decision making for this relatively common disease entity. Given the rarity of this cancer and absence of standard of care with acceptable therapeutic efficacy, a two experimental arm design is justified.

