the setting of resected Stage III or Stage IV NED in CA209007, a nonsignificant trend for improved RFS was observed in PD-L1-positive subjects versus PD-L1-negative subjects at both a 1% and 5% tumor cell expression cut-off⁴⁵. Therefore, PD-L1 expression may be a prognostic marker that may also predict for nivolumab clinical activity.

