4 INVESTIGATIONAL PLAN

4.1 Study Design and Duration

The study design schematic is presented in Figure 3.1-1.

Figure 4.1-1: Study Design Schematic

The subjects will be treated in both arms until disease progression, unacceptable toxicity, or subject withdrawal of consent.

This study will consist of three phases: screening, treatment, and follow-up. For a complete list of study required procedures, please refer to [Section 5](#).

Screening Phase:

- Begins by establishing the subject's initial eligibility and signing of the informed consent form (ICF).
- Subject is assessed for complete study eligibility within the required timeframe found in Table 7.1-1.
- A pregnancy test for WOCBP should be documented within 24 hours prior to the start of the first dose of study medication.
- All subjects must have at least 2 distinct lesions as documented by a complete physical examination or imaging studies within 4 weeks prior to randomization. Imaging studies must include a CT scan of the involved disease sites and all known sites of resected disease and brain magnetic resonance (MRI) or CT (brain CT allowable if MRI is contraindicated or if there is no known history of resected brain lesions).

Treatment Phase:

- Following confirmation of the subject's eligibility, the randomization call to the Moffitt Cancer Center Biostatistics Core can be made. The subject is randomly assigned to the Arm A (nivolumab + ipilimumab) or Arm B (nivolumab + ipilimumab + SBRT).
- Within 2 weeks from randomization the subject must receive the first dose of study medication (Day 1 of Week 1)
- On-study laboratory assessments should be drawn within 72 hours prior to dosing
- Adverse event assessments for grade ≥ 2 toxicities should be documented at each clinic visit and WOCBP must have a pregnancy test every four weeks +/- 1 week.
- Treated subjects will be evaluated for recurrence every 12 weeks +/- 7 days
- Patient Reported Outcome (PRO) instruments must be completed after randomization, prior to the dose of study therapy.

Follow-up Phase:

- Begins after 1 year of treatment or when the decision is made to discontinue a subject from study therapy.
- Patient may continue on the study drug under the treatment protocol indefinitely during the follow-up phase.
- After completion of the first two follow-up visits, subjects will be followed every 3 months for survival.

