9.3.2.2 Secondary Endpoint Methods

The PFS analyses will be conducted using a two-sided log-rank test stratified by prior immunotherapy exposure in randomized subjects. The hazard ratio and corresponding two-sided 95% CI will be estimated using a Cox proportional hazards model, with treatment group as a single covariate, stratified by the above factors. PFS curves, PFS medians with 95% CIs, and PFS rates at 6, 12, 24 and 36 months with 95% CIs will be estimated using Kaplan-Meier methodology.

The OS analysis will be conducted using a two-sided log-rank test stratified by prior immunotherapy exposure at screening in randomized subjects. The hazard ratio and corresponding two-sided (1-adjusted α)% CI will be estimated using a Cox proportional hazards model, with treatment arm as a single covariate, stratified by the above factors. OS curves, OS medians with 95% CIs and OS rates at 12 and 24 months with 95% CIs will be estimated using Kaplan-Meier methodology.

The local control (LC) of irradiated lesions will be conducted using a two-sided log-rank test stratified by prior immunotherapy exposure at screening in randomized subjects. The hazard ratio and corresponding two-sided (1-adjusted α)% CI will be estimated using a Cox proportional hazards model, with treatment arm as a single covariate, stratified by the above factors. LC curves,

LC medians with 95% CIs and LC rates at 12 and 24 months with 95% CIs will be estimated using Kaplan-Meier methodology.

To evaluate PD-L1 expression as a predictive biomarker, a Cox proportional hazards model will be used to test the interaction between PD-L1 expression (positive vs negative) and treatment arm for the primary and secondary endpoint. Additionally, ORR will be analyzed within each PD-L1 expression subgroup (positive and negative) including log-rank tests and hazard ratios with corresponding confidence intervals. PFS curves and medians will be estimated using Kaplan-Meier methodology. These analyses will be descriptive and not adjusted for multiplicity.

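### The PD-L1-by-arm interaction can show only whether PD-L1 modifies the SBRT effect; the two arms cannot separate predictive from prognostic value for nivolumab or ipilimumab, which both arms receive

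*Combined protocol and SAP*

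**What the plan says.** The secondary objective in Section 1.3.2 is "To evaluate whether PD-L1 expression is a predictive biomarker for ORR". The rationale in Section 1.4.9 concerns the drug: "PD-L1 expression may be a prognostic marker that may also predict for nivolumab clinical activity". Section 7.5 likewise opens with factors that might predict response to nivolumab, and then states that "analyses of markers between the two treatment arms will provide the necessary data to identify and validate biomarkers with predictive vs prognostic value".

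For the analysis, Section 9.3.2.2 says that "a Cox proportional hazards model will be used to test the interaction between PD-L1 expression (positive vs negative) and treatment arm". It adds an analysis of ORR within each PD-L1 subgroup, including log-rank tests and hazard ratios, and calls all of this descriptive and unadjusted for multiplicity.

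On the treatments, the Synopsis gives the same drug text for Arm A and Arm B: "Nivolumab 240 mg IV over 30 min q2 weeks and Ipilimumab 1 mg/kg IV over 30 min q6 weeks". Arm B adds SBRT, and Sections 4.1 and 5.5.1 agree. Section 1.4.4 says "we propose a randomized phase II trial in which both arms of the trial are experimental", so any comparison with patients not given both drugs is historical.

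**The concern.** The question posed is whether PD-L1 predicts response to nivolumab. The test compares the PD-L1 effect between two arms that both receive nivolumab and ipilimumab, so it answers a different question: does PD-L1 change what SBRT adds?

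Two misreadings become possible. A marker that tracks response to the drugs equally in both arms gives the interaction test nothing to detect, so a non-significant result could be taken as evidence against PD-L1. A significant interaction could be taken as prediction of nivolumab benefit when it concerns SBRT. Meanwhile, the comparison that bears most directly on the ORR objective, response in PD-L1 positive against PD-L1 negative patients, has no specified method.

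**Working it through.** **Inputs from the documents.** 24 patients per arm at full enrolment (9.1.1), so 48; the Synopsis says "Approximately 50 subjects will be randomized 1:1 and stratified by prior immunotherapy exposure". PD-L1 positivity is 53.8% overall and 75% in Stage IV (Table 1, Section 1.2.1). Tests are two-sided at 0.05 (Synopsis, Analyses).

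**Assumed, not in the documents.** Response rates by PD-L1 status; for the time-to-event check, a median PFS of 6 months in PD-L1 negative Arm A patients and a marker hazard ratio of 0.4.

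**The plan's own figure.** The documents give no power for the PD-L1 test. The stated design power for selecting Arm B (85% at 40% versus 17%) recomputes to 85.5% and is not in question here.

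**Step 1: what the interaction estimates.** Let S = 1 for SBRT and M = 1 for PD-L1 positive:

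logit Pr(response) = a + b·S + m·M + c·S·M

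The interaction test is of c = 0, where c is the log odds ratio for PD-L1 in Arm B minus that in Arm A. The coefficient m is the PD-L1 association under nivolumab plus ipilimumab, and m = m(prognostic) + m(predictive for the drugs). Splitting that sum needs patients without the drugs, and there are none. So m can be estimated but its split cannot, and c concerns SBRT only. A Cox model with the same terms behaves the same way.

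**Step 2: a marker that acts equally in both arms.** At 50% versus 10%, the odds ratio in each arm is (0.50/0.50)/(0.10/0.90) = 9, so c = ln 9 − ln 9 = 0. At 40% versus 17% it is (0.40/0.60)/(0.17/0.83) = 3.25 in each arm, and again c = 0. The size of the marker effect drops out.

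**Step 3: expected counts in 48 patients.** At 53.8% positivity: 25.8 positive and 22.2 negative. At 75%: 36 and 12.

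**Step 4: rejection rates for ORR.** The logistic interaction is a likelihood-ratio test, simulated with 4,000 trials per setting (range over repeat runs). The pooled test is an unstratified Fisher test.

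| ORR, PD-L1 positive vs negative (both arms) | Test | 53.8% positive | 75% positive |
|---|---|---|---|
| 50% vs 10% | PD-L1-by-arm interaction | 5.6% | 2.9% to 3.8% |
| 50% vs 10% | Pooled positive vs negative | about 84% | about 68% |
| 40% vs 17% | Pooled positive vs negative | about 34% | about 23% |

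A more conservative interaction test (Wald, 0.5 added per cell) rejects in 1.0% to 2.2% of trials at 40% versus 17%.

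**Step 5: the Cox model that the plan names.** With 50 patients, a marker hazard ratio of 0.4 in both arms and no SBRT effect, the interaction rejects in 6.7% (53.8% positive) and 5.1% (75% positive) of trials. With no marker effect at all it rejects in 6.6%. The arm-adjusted PD-L1 effect is detected in 85.5% and 75.5%. Adding an SBRT hazard ratio of 0.7 gives 6.3% and 4.7% for the interaction.

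**Step 6: what the interaction can find.** If PD-L1 does modify the SBRT effect, with a ratio of hazard ratios of 0.5, power is 24% (53.8% positive) or 18% (75% positive). For 80% power with four equal cells, events needed = 16 × (1.960 + 0.842)² / (ln 0.5)² = 16 × 7.85 / 0.480, about 261. The trial can yield about 50.

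**The case against.** The strongest reply is that the plan covers more than the interaction. Section 1.3.3 explores biomarkers associated with ORR, PFS and OS. Section 7.5 mentions associations with outcome just before the sentence at issue. Section 9.2.2 measures the PD-L1 endpoint as RFS by expression level. Section 9.3.2.2 analyses ORR within each PD-L1 subgroup, which would ordinarily put both rates on the page. A reader might infer that the plan ignores marker-outcome association, or that a strong PD-L1 relation would go unseen and the objective be reported as negative. These passages do not support that. What stands is narrower: no positive-versus-negative ORR comparison is specified for the secondary objective, and the log-rank tests and hazard ratios named for the subgroups are most naturally read as arm contrasts.

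The interaction is also a fair question in its own right. Sections 1.2.2 and 1.2.3 link PD-L1 to resistance to radiation plus ipilimumab, and Section 7.5.1 seeks predictors of SBRT efficacy as well as drug efficacy. For SBRT, the randomized factor, the arm interaction is the right test of prediction, and the 7.5 sentence is true in that sense. This stands, and it is why the interaction should be kept and relabelled.

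Finally, the 50% versus 10% split is an assumption. At 40% versus 17% the pooled test would usually miss significance too, and the pooled figures are for an unstratified test. This also stands: pooling addresses the right quantity, but it does not guarantee a clear answer.

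**Conclusion.** Wrong as written for nivolumab and ipilimumab. The conclusion follows from both arms sharing the same drugs and does not depend on sample size or effect size: the planned interaction addresses modification of the SBRT effect, and this design cannot separate predictive from prognostic value for the two drugs.

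A reader might go further and infer that a marker governing response to these drugs must test negative. The documents do not support that. Rejection at about the chance rate requires the PD-L1 effect to be equal in both arms on the model's scale, and PD-L1 may also modify the SBRT effect. Even then, a significant interaction would describe SBRT benefit.

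The percentages are illustrations under assumed marker effects and should be read as a range. The consequence is limited: the PD-L1 analyses are descriptive, and the two-stage and pick-the-winner decision in Section 9.1.1 does not use PD-L1.

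**What to change.** 1. In Section 9.3.2.2, add for the ORR objective a comparison of response in PD-L1 positive versus negative patients pooled over both arms, with response defined as for the primary endpoint. Adjust for arm and, where numbers allow, prior immunotherapy. Report the difference in ORR with its 95% CI. The caveat on numbers matters: at 75% positivity there are about 12 PD-L1 negative patients, or 3 in each of four arm-by-prior-therapy strata if evenly spread.
2. Keep the PD-L1-by-arm interaction as a descriptive analysis, labelled *modification of the SBRT effect*.
3. In Section 7.5, replace the claim with a statement that the trial can assess association with outcome under nivolumab plus ipilimumab, and modification of the SBRT effect, but cannot separate predictive from prognostic value for nivolumab or ipilimumab.

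The cost is wording changes and one extra analysis of data already collected. The downside is a more modest claim: association in place of prediction for the drugs.
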